10.1.13 Clinical Monitoring

Clinical site monitoring will be conducted by the sponsor representative to ensure that the rights and well-being of study subjects are protected, that the reported study data are accurate, complete, and verifiable, and that the conduct of the study is in compliance with the currently approved protocol/amendment(s), with ICH-GCP, and with applicable regulatory requirement(s).

Before the study begins, a monitor representing the sponsor will visit the investigational site to determine the adequacy of the facilities and to discuss with the principal investigator(s) and other personnel involved in the study their responsibilities with regard to protocol adherence, and the responsibilities of the sponsor or its representatives.

During the study, a monitor representing the sponsor will have regular contact with the investigational site, including visits to:

- provide information and support to the principal investigator(s)
- confirm that facilities remain acceptable
- confirm that the investigational team is adhering to the protocol
- confirm that data are being accurately recorded in the eCRF
- confirm that the study is conducted according to the ICH-GCP
- confirm that an update of the screening log is performed, and that investigational product accountability checks are being performed
- Perform source data verification (a comparison of the data in the eCRFs with the subject's records at the hospital or practice, and other records relevant to the study.)

This will require direct access to all original records for each subject (e.g., clinic charts).

The monitor, medical monitor or the sponsor representatives will be available between visits if the principal investigator(s) or other staff at the investigational site need information and advice.

10.1.14 Data Quality Assurance

In order to verify the proper conduct of the clinical study, which is compliant with this protocol as well as ICH-GCP and related notifications, and data reliability, the sponsor will perform quality control according to the SOP that are defined separately.

In order to ensure the conduct of the clinical study, as well as the creation, recording, and reporting of data are compliant with this protocol as well as ICH-GCP and related notifications, the sponsor will conduct audits that are performed by a controller of audit/auditor, who is independent of the department involved in the clinical study, in the company and the study institution or an outsourcing contractor as needed, according to the SOP that are defined separately.

At the request of a monitor, controller of audit/auditor, the IRB/IEC, or the regulatory authority, the principal investigator/the study institution head will provide direct access to all the records related to the clinical study, including source documents.

10.1.15 Data Collection and Management Responsibilities

The management of data and each specific data point will be determined before data are locked, through discussion(s) with medical specialists and statisticians, as needed.

Data collection is the responsibility of the clinical study staff at the site under the supervision of the principal investigator. The principal investigator is responsible for ensuring the accuracy, completeness, legibility, and timeliness of the data reported.

All source documents should be completed in a neat, legible manner to ensure accurate recording of data in the eCRF.

Data recorded in the eCRF derived from source documents should be consistent with the data recorded on the source documents.

Clinical data (including AEs and concomitant medications) will be entered into an eCRF, a 21 CFR Part 11-compliant data capture system. The data system includes password protection and internal quality checks to identify data that appear to be inconsistent, incomplete, or inaccurate. Clinical data will be entered directly into the eCRF from the source documents. For completion/correction of the eCRF, refer to the separate sponsor manual.

10.1.16 Source Documents

JCR Pharmaceuticals Co., Ltd. is the sponsor for the JR-171-101 study. Subject data will be registered at the study site. The sponsor will supply the study site with all necessary material and eCRF at the initiation of the study. Each eCRF and the subject's medical records will be verified carefully by monitors representing the sponsor to ensure full protocol compliance with the planned procedures with to regard to data completion and follow-up. The sponsor provides project oversight at all times. A project representative from the sponsor will be available to the study sites by telephone and/or by visit.

The principal investigator is responsible for completing the eCRF forms and including all relevant data. The eCRF forms will be monitored by representatives of the sponsor who will contact the principal investigator should the need arise for further clarification. Data lists will be generated from the database enabling a direct comparison between the original case report forms and the database. This will facilitate the clarification of any errors. These corrected documents, and other study documents, will be retained as the final study documentation.

The principal investigator must arrange for the retention of the ID codes of subjects (*i.e.*, hospital/unit code, study ID code and study number) for as long as the sponsor requests after completion or discontinuation of the clinical study. Other source documents, such as subject files and clinic case notes, must be retained for the maximum period of time permitted by the hospital, institution or private practice and if this is less than the sponsor requires after the completion or discontinuation of the clinical study, then the sponsor must be notified to arrange record retention.

If the principal investigator relocates or retires, or otherwise withdraws his/her responsibility for maintaining the study documentation, the sponsor must be notified in writing so that adequate provision can be made with regard to the ID codes of subjects, copies of the study documentation (e.g., copies of eCRFs) and other source data (if available). This responsibility may be transferred to the sponsor, who will make arrangements to store the data. An inventory of stored data will be held by the principal investigator and a copy by the sponsor.

Data without a written or electronic record will be identified before study start and should be recorded directly on the eCRF, which will be documented clearly as being the source data.

10.1.17 Storage of Records and Other Documents

The principal investigator/institute shall store the essential documents and records related to the clinical trial for either of the following periods, 1 or 2, whichever comes later.

- The sponsor specific essential documents should be retained until at least 2 years after the last approval of a marketing application in an ICH region and until there are no pending or contemplated marketing applications in an ICH region. These documents should be retained for a longer period however if required by the applicable regulatory requirement(s) or if needed by the sponsor.
- 2. If the sponsor discontinues the clinical development of an investigational product (*i.e.*, for any or all indications, routes of administration, or dosage forms), the sponsor should maintain all sponsor-specific essential documents for at least 2 years after formal discontinuation or in conformance with the applicable regulatory requirement(s).

Principal investigators/institutes take measures to ensure that these records are stored

appropriately during this storage period and that they can be retrieved on request. No records will be destroyed without the written consent of the sponsor.

10.1.18 Study and Site Start and Closure

The first act of recruitment will be after the first site open.

The sponsor designee reserves the right to close the study site or terminate the study at any time for any reason at the sole discretion of the sponsor. Study sites will be closed upon study completion. A study site is considered closed when all required documents and study supplies have been collected and a study-site closure visit has been performed by the sponsor.

The principal investigator may initiate study-site closure at any time, provided there is reasonable cause and sufficient notice is given in advance of the intended termination.

Reasons for the early closure of a study site by the sponsor or principal investigator may include but are not limited to:

- Failure of the principal investigator to comply with the protocol, the requirements of the IRB/IEC or local health authorities, the sponsor's procedures, or ICH-GCP guidelines
- Inadequate recruitment of subjects by the principal investigator
- Discontinuation of further study intervention development

If the study is prematurely terminated or suspended, the sponsor shall promptly inform the Principal Investigators, the IECs/IRBs, the regulatory authorities, and any contract research organization(s) used in the study of the reason for termination or suspension, as specified by the applicable regulatory requirements. The principal investigator shall promptly inform the subject and should assure appropriate subject therapy and/or follow-up.

10.1.19 Publication Policy

When publishing an academic paper or making a presentation at a conference in relation to this clinical study, the principal investigator will obtain prior written approval from the sponsor. Note that a patent, manufacturing method, and pharmaceutical formulation related to this investigational product will not be disclosed without approval of the sponsor.

The sponsor has the right to use the result of this clinical study to promote sales after obtaining approval.

10.1.20 Conflict of Interest Policy

Any actual conflict of interest of the principal investigator, subinvestigator or persons who have a role in the design, conduct, analysis, publication, or any aspects of this clinical study will be disclosed and managed. Furthermore, persons who have a perceived conflict of interest will be required to have such conflicts managed in a way that is appropriate to their participation in the study.

10.1.21 Additional considerations

It is not applicable for the JR-171-101 study.

JR-171 Phase I/II study Version 6.00 Protocol number: JR-171-101 12 November 2021

10.2 Appendix 2: Adverse Events: Definitions and Procedures for Recording, Evaluating, Follow-up, and Reporting

10.2.1 Definition of AE

AE Definition

An AE is any untoward or unintended illness or its sign (including an abnormality observed in laboratory tests or physiological tests) in a subject, which does not necessarily have to have a causal relationship with the investigational product. AEs that occur after the administration of an investigational product, those that have an undeniable causal relationship with the investigational product are considered adverse drug reactions.

- Any patient having received any amount of investigational product should be evaluated for safety. The schedule of assessments is shown in the Schedule of Activities, Section 1.3.
- Any AE must be documented and the following guidelines will be used for this purpose. An AE is the development of an undesirable medical condition or the deterioration of a pre-existing medical condition following or during exposure to a pharmaceutical product, whether or not considered causally related to the product. An undesirable medical condition can be symptoms (e.g., nausea, chest pain), signs (e.g., tachycardia, enlarged liver) or the abnormal results of an investigation (e.g., laboratory findings, electrocardiogram). In clinical studies, an AE can include an undesirable medical condition occurring at any point of time after the patient consented to participate. This definition includes intercurrent illnesses or injuries, and exacerbation of pre-existing conditions.
- Where a diagnosis is possible, it is preferable to record it in the eCRF rather than as a series of terms relating to the diagnosis.
- An event that is solely due to progression of disease should not be reported as AEs.

Events Meeting the AE Definition

- Any abnormal laboratory test results (hematology, clinical chemistry, or urinalysis) or other safety assessments (e.g., ECG, radiological scans, vital signs measurements), including those that worsen from the time of informed consent, considered clinically significant in the medical and scientific judgment of the principal investigator or subinvestigator (i.e., not related to progression of underlying disease).
- Exacerbation of a chronic or intermittent pre-existing condition including either an increase in frequency and/or intensity of the condition.
- New conditions detected or diagnosed after study intervention administration even though it may have been present before the start of the study.
- Signs, symptoms, or the clinical sequelae of a suspected drug-drug interaction. Signs, symptoms, or the clinical sequelae of a suspected overdose of either the study intervention or a concomitant medication. An overdose, per se, will not be reported as an AE/SAE unless it is an intentional overdose undertaken with possible suicidal/self-harming intent. Such overdoses should be reported regardless of sequelae.
- The signs, symptoms, and/or clinical sequelae resulting from lack of efficacy should be reported as AE or SAE if they fulfil the definition of an AE or SAE. Also, "lack of efficacy" or "failure of expected pharmacological action" also constitutes an AE or SAE.

Events NOT Meeting the AE Definition

- Any clinically significant abnormal laboratory findings or other abnormal safety
 assessments which are associated with the underlying disease, unless judged by the
 principal investigator to be more severe than expected for the subject's condition.
- The disease/disorder being studied or expected progression, signs, or symptoms of the disease/disorder being studied, unless more severe than expected for the subject's condition.
- Medical or surgical procedures (**e.g.**, endoscopy, appendectomy): the other condition that leads to the procedure is the AE.
- Situations in which an untoward medical occurrence did not occur (social and/or convenience based admission to a hospital).

Events NOT Meeting the AE Definition

 Anticipated day-to-day fluctuations of pre-existing disease(s) or condition(s) present or detected at the start of the study that do not worsen.

10.2.2 Definition of Clinically Relevant Changes in Laboratory Assessments

Criteria for clinically relevant changes in laboratory test values

- When the value varies from within the reference range to outside the reference range
- When the value outside the reference range changes in the discretion of deterioration
- When the value varies from outside the reference range to outside the reference range

10.2.3 Definition of SAE

If an event is not an AE per definition above, then it cannot be an SAE even if serious conditions are met (serious condition; e.g., hospitalization for signs/symptoms of the disease under study).

An SAE is defined as any untoward medical occurrence that, at any dose:

a. Results in death

b. Is life-threatening

In the opinion of the principal investigator or subinvestigator, the AE places the patient at immediate risk of death from the event as it occurred; it does not include a reaction that, had it occurred in a more severe form, might have caused death.

- c. Requires inpatient hospitalization or prolongation of an existing hospitalization, unless the hospitalization is for;
 - Admission for treatment that was scheduled before the clinical study or that for examinations
 - Monitoring of the studied indication, not associated with any deterioration in condition
 - Social reasons and respite care in the absence of any deterioration in the patient's general condition

d. Results in persistent or significant disability or incapacity

e. A congenital anomaly or birth defect

f. Other situations:

 An important and significant medical event that, based upon appropriate medical judgment, may jeopardize the patient or may require medical or surgical intervention to prevent one of the other outcomes listed above

10.2.4 Recording and Follow-Up of AE and/or SAE

AE and SAE Recording

- In the event of an AE/SAE, the name of the AE, severity, seriousness, the date of
 occurrence, whether or not there was a procedure for the administration of the
 investigational product as well as its details, the outcome of the AE (including the date of
 its determination), a causal relationship between the AE and the investigational product,
 and comments as needed should be recorded in the eCRF.
- It is the responsibility of the principal investigator or subinvestigator to document any AE
 occurring from the time of informed consent obtained in the subject's hospital notes and in
 the eCRF. MedDRA will be used to code AEs by the data management and
 pharmacovigilance groups.

Assessment of Severity

The principal investigator or subinvestigator will determine the severity of AEs reported on the eCRF as follows:

If the AE is listed in the CTCAE Version 5 table, then the highest level that the AE reached should be noted. If the AE is not listed in the CTCAE Version 5, then the highest level reached should be noted, according to the following description:

Assessment of Severity

- Grade I = Slight: An AE, which is easily tolerated by the patient. It only incurs a
 minimum of discomfort and does not influence ordinary daily tasks.
- Grade II = Moderate: An AE, which is of sufficient severity to have a negative influence on ordinary daily tasks.
- Grade III = Severe: An AE, which effectively hinders ordinary daily tasks.
- Grade IV = Life threatening: An AE, which puts the patient's life at risk.
- Grade V = Death: Death related to AE.

Assessment of Causality

• The principal investigator or subinvestigator are obligated to assess the relationship between study intervention and occurrence of each AE/SAE.

Related: The causal relationship between the investigational product and the AE may be at least reasonable and may not be denied because of disappearance after discontinuation of administration, recurrence after resumption of administration, establishment of a causal relationship with the investigational product or similar drug, absence of confounding risk factors, consistency with exposure and duration of exposure, almost definite explanation for the contribution of the investigational product by supporting an accurate medical history, and lack of reasonable possibility of causal relationship between the concomitant medications/therapies and the AE.

Unrelated: in cases other than the above.

- The principal investigator or subinvestigator will use clinical judgment to determine the relationship.
- Alternative causes, such as underlying disease(s), concomitant therapy, and other risk
 factors, as well as the temporal relationship of the event to study intervention administration
 will be considered and investigated.
- The principal investigator or subinvestigator will also consult the Investigator's Brochure and/or Product Information for marketed products, in his/her assessment.
- For each AE/SAE, the principal investigator or subinvestigator must document in the medical notes that he/she has reviewed the AE/SAE and has provided an assessment of causality.
- There may be situations in which an SAE has occurred and the principal investigator or subinvestigator have minimal information to include in the initial report to sponsor. However, it is very important that the principal investigator or subinvestigator always make an assessment of causality for every event before the initial transmission of the SAE data to sponsor.
- The principal investigator or subinvestigator may change his/her opinion of causality in light of follow-up information and send a SAE follow-up report with the updated causality assessment.
- The causality assessment is one of the criteria used when determining regulatory reporting requirements.

Assessment of Outcome

The outcome of an AE will be determined according to the criteria described below.

Outcome

Recovery	Disappearance of symptoms/findings, normalization of laboratory values or recovery to values measured at baseline
Remission	Reduction in severity, disappearance of the most part of symptoms/findings, recovery of laboratory values to a level close to values measured at baseline
Unrecovered	No changes in symptoms/findings or laboratory values
Recovered with sequelae	Dysfunction that can interfere with daily activities
Death	Death

Follow-up of AEs and SAEs

- The principal investigator or subinvestigator will continually monitor any subject with an AE and SAE until either the event has returned to the baseline grade or ≤Grade I; or if the AE is determined to be chronic, a cause is identified.
- If a subject has an ongoing AE at Week 5 in Part 1/Week 13 in Part 2 or discontinuation, then the subject will be followed until a time when the principal investigator or subinvestigator judges that the clinical condition of the subject is stable and safety can be ensured, or when a causal relationship with the investigational product is not found. The follow-up as part of the clinical study may be terminated at 4 weeks (28 days) after the completion (discontinuation) of the clinical study.
- Follow-up of all AEs must be documented in the subject's medical record and on the eCRF.
- When a subject withdraws from participation in the study before the first administration, a follow-up with the subject is unnecessary.

Reporting events to subjects

If any event could disturb the subject's daily activities, such an event should also be presented to the subject promptly to confirm their willingness to continue study participation.

Management of pregnancy

In case of the subject's or the subject's partner's pregnancy after the administration of an investigational product, it should be reported to the sponsor as soon as possible and followed for the full duration of the pregnancy and/or until outcome is known. If a miscarriage or stillbirth occurs as a result of pregnancy, it should be reported to the sponsor within 24 hours of becoming aware. These kinds of events should be reported per the SAE reporting process indicated in Section 10.2.5.

In case of a subject's partner's pregnancy, the principal investigator or subinvestigator must obtain the signed and dated informed consent from the subject's partner before collecting necessary information about her pregnancy.

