7.1 Discontinuation of Study Intervention

7.1.1 Criteria for Termination or Suspension

The sponsor will consider the discontinuation/cessation of the whole or part of the clinical study in any situation described in the information below. In this case, all principal investigators will be immediately informed by the sponsor.

- 1. Occurrence of a serious adverse event (SAE) with CTCAE grade ≥ IV
- 2. Occurrence of serious adverse drug reactions coded to same preferred term (PT) in 2 or more subjects
- 3. A research report that suggests the tendency of occurrence of adverse drug reactions,

JR-171 Phase I/II study Version 6.00 Protocol number: JR-171-101 12 November 2021

such as the number of reactions that occur, the frequency of occurrence, and occurrence conditions, have significantly changed

- 4. A research report that shows the clinical study may cause serious diseases including cancer, disabilities, or death
- 5. When the clinical study suggests that there is no efficacy of JR-171 in this population
- 6. A research report that demonstrates that there is no efficacy or effectiveness for the disease that the clinical study aims to treat
- 7. When either the sponsor, the study institution, or the principal investigator has committed a grave breach of ICH-GCP, the protocol, or the contract, leading to a situation where the proper continuation of the clinical study is considered problematic
- 8. When the continuation of the clinical study is considered difficult due to changes of the structure or environment for conducting the clinical study (e.g., a transfer of the principal investigator)
- 9. Other cases in which the continuation of the clinical study is considered inappropriate due to new information or a change in the situation identified during the clinical study

When the clinical study is discontinued the following examinations/observations described below are to be performed as much as possible, if the subject agrees, after final administration of the investigational product. The details should be recorded in the eCRF listed below except for items 3, 4, 5, 7 and 9, it is not necessary to record measurements in the eCRF. The date of discontinuation and the reason for discontinuation will also be recorded in the eCRF.

- 1. Vital signs (pulse rate, body temperature, blood pressure, respiratory rate and percutaneous oxygen saturation)

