7.2 Subject Discontinuation/Withdrawal from the Study

Subjects are free to withdraw from participation in the study at any point of time upon request

JR-171 Phase I/II study Version 6.00 Protocol number: JR-171-101 12 November 2021

to the principal investigator. Subjects who are prematurely withdrawn from the study will not be replaced.

A principal investigator or subinvestigator may discontinue or withdraw a subject from the study for the following reasons:

- 1. When a subject or his/her legal representative wishes to discontinue the clinical study
- 2. When the continuation of the study became impossible for reasons including a transfer to another hospital/change of address during the clinical study
- 3. When a subject was found to be ineligible after the start of the clinical study such that continued participation would compromise safety of the subject or integrity of the study
- 4. When the continuation of the clinical study becomes impossible for reasons including the occurrence of an AE*
- 5. When a subject experiences anaphylactic shock
- 6. Other cases in which the principal investigator or subinvestigator deems it necessary to discontinue the clinical study because compliance with the protocol has become difficult

*When the occurrence of an SAE with CTCAE grade ≥ IV, the principal investigator or subinvestigator should consider the discontinuation/temporary cessation of the study. If the principal investigator or subinvestigator can rule out a causal relationship with JR-171 based on the additional information and CTCAE grade improved to III or less, administration could be resumed, but otherwise subjects must be discontinued.

For examinations/observations at the time of the subject discontinuation from the study, see Section 7.1.1.

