Caution: These criteria describe so-called classic cases of anaphylaxis. Other presentations may also indicate anaphylaxis (e.g., early presentation, generalized flushing; isolated presentation, sudden hypotension only in a patient without evidence of allergen exposure; classic presentation but with a non-allergenic cause, such as exercise). Conversely, clinicians need to remember the potential for false-positive symptoms or signs (e.g., difficulty breathing from panic, faintness from vasovagal episode).

*Low systolic blood pressure for children is defined as <70 mm Hg from 1 month to 1 year; less than (70 mm Hg + $(2 \times age)$) from 1 to 10 years; and <90 mm Hg from age 11 to 17 years.

• IAR¹⁷)

Reactions harmful to the living body that are caused by administration of the infusion, occurring during or within 24 hours after completion of the infusion (*e.g.*, chill, fever, a feeling of body temperature fluctuation, nausea, high blood pressure).

Also, in addition to reported SAEs, all the events that have significantly abnormal laboratory values or require such action as the discontinuation, temporary cessation, or addition of important combination therapy with respect to the investigational product should be evaluated as significant AEs.

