10.1.3 Financial Payment and Insurance

With respect to any liability directly or indirectly caused by the investigational products in connection with this clinical trial, the sponsor assumes liability by law on behalf of the principal investigator(s) and his/her assistants, only in cases that meet all of the following; the principal investigator(s) and his/her assistants have followed the instructions of the sponsor in accordance with this protocol and any amendments; the investigational products administered to the subject in this clinical trial have been supplied by the sponsor; the principal investigator and his/her assistants have performed this clinical study in accordance with current medical and scientific practice.

A letter of indemnity will be signed between the sponsor and the principal investigator(s) (between the sponsor and the head of the medical institution in countries where applicable), and the sponsor will insure according to local requirements.

Compensation for health damages

When the causal relationship between the JR-171 administration and the health damage cannot be reasonably ruled out, the sponsor compensates for the health damage unless it is caused for any reason attributable to the medical institution or subject.

Medical cost

In the event of study-related health damage, the patient's out-of-pocket expenses excluding benefits from health insurance, etc. shall be reimbursed by the sponsor.

Compensation claim

In the event that a request for compensation from a subject has been filed or a matter subject to compensation is suspected, the participating medical organization should immediately contact the sponsor. The sponsor will respond promptly in accordance with the SOP for health damage compensation for test subjects in-house.

Insurance

The sponsor will purchase insurance to ensure the performance of these procedures.

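### The causality definition in Section 10.2.4 does not say whether one or all of its seven grounds make an event Related, so possible reactions to JR-171 could be labelled Unrelated or classified differently across sites

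*Combined protocol and SAP*

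**What the plan says.** Causality is a two-level scale, defined under Assessment of Causality in Section 10.2.4. Related begins permissively: the relationship "may be at least reasonable and may not be denied because of disappearance after discontinuation of administration, recurrence after resumption of administration". The list then continues, and its last two grounds are "almost definite explanation for the contribution of the investigational product by supporting an accurate medical history, and lack of reasonable possibility of causal relationship"; the second of these refers to other treatments the subject is receiving. The other category is purely residual: "Unrelated: in cases other than the above". The bullets that follow tell the investigator to use clinical judgment and to consider alternative causes and timing.

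Three other sections use causal wording at their own levels:
- Section 10.2.1, on events after dosing: "those that have an undeniable causal relationship with the investigational product are considered adverse drug reactions".
- Section 10.1.3, on compensation, applies when the link between "the JR-171 administration and the health damage cannot be reasonably ruled out".
- Section 7.2, on resuming after a serious event of grade IV or higher, asks whether the investigator "can rule out a causal relationship with JR-171 based on the additional information".

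**The concern.** The definition holds two thresholds in one sentence. The opening is close to a standard of not being able to exclude the drug. The list contains items close to proof and closes with a conjunction. Nothing says that any one ground is enough, that the list gives examples, or that all grounds must be met. There is no intermediate category, so whatever fails the chosen reading becomes Unrelated.

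The label matters in several places:
- Relationship to JR-171 is part of the first-listed primary endpoint (Sections 1.1 and 3).
- Suspension criterion 2 in Section 7.1.1 is "Occurrence of serious adverse drug reactions coded to same preferred term (PT) in 2 or more subjects".
- Section 8.3.1 collects events in the 28 days after the last visit only if they are considered related.
- Section 10.2.4 lets follow-up of an ongoing event end when no causal relationship is found.
- Sections 10.2.4 and 10.2.5 use causality to decide regulatory reporting.

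With six planned sites in three countries and about 19 subjects, a few events read differently can change these results.

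**Working it through.** The documents give no figure on this point, so there is none to reproduce. The check compares the text with the plan's other rules, then gives two illustrations under stated assumptions.

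**Step 1: the seven grounds.** In order, they are: (1) the event goes away on stopping; (2) it returns on resuming; (3) a causal link is already established for this or a similar drug; (4) no confounding risk factor; (5) it fits the exposure and its duration; (6) a near-definite explanation involving the product; (7) no reasonable possibility that concomitant treatment is the cause.

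**Step 2: can all seven be met in this study?** Not always.
- *Anaphylactic shock.* Section 6.1 requires the infusion to be stopped and the subject discontinued. Ground 2 then cannot be observed.
- *Initial SAE reports.* Section 8.3.1 sets a 24-hour limit. Section 10.2.4 requires a causality assessment before the first transmission, even on minimal information. Ground 2, and often ground 1, will not be known by then. The assessment may be revised later, but the first report carries the first label.
- *Events starting after a subject's last infusion.* Ground 2 cannot be met by a later infusion within this study. With full dosing, that is the period after 4 of 4 × 4 = 16 infusions in Part 1 (25%) and about 15 of 15 × 12 = 180 in Part 2 (8.3%).

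On the all-grounds reading such events become Unrelated. On the any-one reading they can be Related.

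**Step 3: how far apart the readings are.** Assume that each ground is met independently with probability p for an event JR-171 truly caused. Then P(all seven) = p^7 and P(at least one) = 1 − (1 − p)^7.
- p = 0.70: 0.082 against 0.9998
- p = 0.80: 0.210 against more than 0.9999
- p = 0.90: 0.478 against more than 0.9999
- p = 0.95: 0.698 against more than 0.9999

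The values of p and the independence are assumptions. Where ground 2 is unobservable, the first probability is zero.

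**Step 4: effect on suspension criterion 2.** Take n = 4 + 15 = 19, a true per-subject rate r of a serious reaction under one preferred term, and a share s of those labelled related. The chance of two or more subjects is 1 − (1 − rs)^19 − 19·rs·(1 − rs)^18.
- r = 5%: 0.245 at s = 1; 0.081 at s = 0.5
- r = 10%: 0.580 at s = 1; 0.422 at s = 0.75; 0.245 at s = 0.5; 0.081 at s = 0.25
- r = 20%: 0.917 at s = 1; 0.580 at s = 0.5

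The values of r and s are assumptions. They show sensitivity to labelling and do not predict what sites will do.

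**The case against.** The best defence is that the definition should be read as a whole. Its operative words are permissive and the list supplies reasons for a judgment. The clinical-judgment bullet, the instruction to consider alternative causes and timing, the demand for a causality call on minimal information and the expectation of related events after dosing has ended all fit weighing better than a checklist. A reading that could never call anaphylactic shock related is hardly what the sponsor intended. This stands as an argument about intent. It does not remove the fault, because the text never says so and the residual category penalises a literal reader.

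The following stronger inferences are tempting, but the documents do not support them.
- *Related events will be under-counted.* That needs the all-grounds reading. The text allows either reading, so it supports a risk of under-counting or of inconsistency between sites.
- *Infusion associated reactions will be under-counted.* Section 8.3.6 defines them separately as "Reactions harmful to the living body that are caused by administration of the infusion", with a 24-hour window, and Section 8.3 records them as an eCRF item in addition to relationship. Nothing ties them to the Related category. The grade III or higher trigger in Section 6.6.1 uses the reaction itself.
- *Almost no Part 1 event can be Related, because each dose is given once per subject.* The ground concerns resumption and sets no same-dose condition. Section 8.2.2 records interruption and resumption within an infusion, and 12 of the 16 planned infusions are followed by another.
- *Permitted pretreatment usually defeats the concomitant-drug ground.* That ground asks about reasonable possibility, not mere presence, and no frequency of pretreatment is given.
- *Sections 7.2 and 10.1.3 set an opposite standard for classifying events.* They govern resumption and compensation. The wording in Section 10.2.1 may also be meant as a relationship that cannot be denied, which would point the same way as the opening of Section 10.2.4.

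The consequences are also bounded. All SAEs go to the sponsor within 24 hours. Suspension criterion 1 needs no causality, and criterion 9 is a catch-all.

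**Conclusion.** The concern holds as an ambiguity in a rule that matters. Section 10.2.4 combines a low opening threshold with a conjunctive list that includes near-proof items, sends the remainder to Unrelated, and sits beside an adverse drug reaction definition in Section 10.2.1 that can be read more strictly still. The same event could be Related at one site and Unrelated at another, and some possible reactions could be labelled Unrelated on a literal reading.

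The effect is confined to counts and decisions that use relatedness. The treatment-emergent incidence tables in Section 9.4.3 take all events after the first dose, so total counts do not change. The documents cannot size the misclassification. The illustrations show that if half of true serious reactions lost the related label, the chance of meeting suspension criterion 2 would fall by 0.16 to 0.34 over assumed rates of 5% to 20% (0.245 − 0.081 = 0.164; 0.580 − 0.245 = 0.335; 0.917 − 0.580 = 0.337). This should be corrected, but it does not undermine the design.

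**What to change.** Use one threshold in Sections 10.2.1 and 10.2.4:
- Related: a causal relationship with JR-171 is a reasonable possibility or cannot reasonably be ruled out.
- Unrelated: a causal relationship can reasonably be ruled out.

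Keep the seven grounds as factors to weigh, and state that none is required. Put the same standard in place of the adverse drug reaction wording in Section 10.2.1. State that infusion associated reaction status is recorded independently of Related. Check that Sections 7.2 and 10.1.3 can be reconciled with the single definition; their own purposes need not change.

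The cost is a wording change in Appendix 2 and in the eCRF completion guide. The downside is a somewhat higher count of related events. If the change is made after events have been classified, those events should be re-assessed under the new wording so that the endpoint rests on one standard; Section 10.2.4 already allows a causality opinion to be revised on follow-up.
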